6.7. STATISTICAL TESTS

Unless otherwise noted, all tests of treatment effects will be conducted at a 2-sided alpha level of 0.05 and/or 2-sided 95% confidence interval (CI).

6.8. PRECISION

All values will be rounded using the SAS® function ROUND, as the last step prior to presentation. All computed percentages (%) will be presented using one decimal place. Categories with a '0' count will not display the percentage (%) value. If the original data has N decimal places (as derived from the raw data), then the summary statistics for quantitative data will contain the following number of decimal places (to a maximum of 3 places):

Minimum and maximum: N Mean and median: N + 1

SD: N+2

P-values greater than or equal to 0.001 and less than or equal to 0.999 will be rounded to 3 significant digits and presented with three decimal places. Any p-value less than 0.001 will be presented as '<0.001', while pvalues greater than 0.999 will be presented as '>0.999'. CIs will be presented to one more decimal place than the raw data.

COMMON CALCULATIONS

For quantitative measurements, change from baseline will be calculated as:

- Test Value at Visit X (Post-baseline visit) Baseline Value
 - If baseline is missing, change from baseline will be presented as missing in the listing. That is, no imputation for change from baseline will be performed.

Calculation of BP Percentile:

"The fourth report on diagnosis, evaluation, and Treatment of High Blood Pressure in Children and Adolescents" (https://www.nhlbi.nih.gov/files/docs/resources/heart/hbp_ped.pdf) will be used to calculate BP Percentile.

6.10. SOFTWARE VERSION

All analyses will be conducted using SAS® version 9.4, or higher, on the WINDOWS 32 bit operating system.

7.0 Document: 2014-000674-18 Statistical Analysis Plan Version 7.0 Version Number:

Version Date:

13JAN2020

Template No.: CS_TP_BS016 Revision 5 Reference: CS_WI_BS005

Effective Date: 01Apr2018

Author:

7. STATISTICAL CONSIDERATIONS

7.1. ADJUSTMENTS FOR COVARIATES AND FACTORS TO BE INCLUDED IN ANALYSES

The following covariates and factors are used in the analyses. For details of their inclusion in the models, see the specific analysis section.

- Week 6/Final Visit of the DB Phase seDBP.
- Baseline seDBP.
- Baseline seSBP.
- Baseline MAP.
- Treatment during DB Phase (AZM low, med, high dose and losartan).
- Treatment during Withdrawal Phase, (AZM low, med, high and placebo).
- Treatment for study drug (AZM low, med, high).
- Age (Tanner stage $<3, \ge 3$).
- Weight (<50 kg, ≥50 kg).
- Race Group (Black or African American, Non- Black or African American).

7.2. MULTICENTER STUDIES

This study will be conducted by multiple investigators at multiple centers internationally. Randomization to treatment arms is not stratified by country/center.

Center pooling will not be carried out for use in analyses for this study.

7.3. MISSING DATA

Missing safety data (not considering dates) will not be imputed.

For efficacy data, two different methods will be used.

- Multiple Imputation: using the Markov Chain Monte Carlo method.
- Last-observation-carried-forward (LOCF): the last post baseline double-blind observed value will be carried forward where data are missing (e.g., the subject has missing data or has dropped out of the study).

Details for how to handle missing efficacy data are in section 15.1 - 15.2 of this analysis plan.

7.4. MULTIPLE COMPARISONS/ MULTIPLICITY

To control for multiplicity of the type 1 error, the following sequential testing procedure will be employed in

7.0 Document: 2014-000674-18 Statistical Analysis Plan Version 7.0 Version Number:

Version Date:

13JAN2020

Template No.: CS_TP_BS016 Revision 5 Reference: CS_WI_BS005

Effective Date: 01Apr2018

Author:

the analysis of the primary endpoint using an analysis of covariance (ANCOVA) model and estimate statements: Step 1, the mean AZM effect versus placebo will be tested, if statistically significant then testing will continue to the next step; Step 2, AZM high dose effect versus placebo will be tested, if statistically significant then testing will continue to the next step; Step 3, AZM med dose effect versus placebo will be tested, if statistically significant then testing will continue to the next step; Step 4, AZM low dose effect versus placebo will be tested.

8. OUTPUT PRESENTATIONS

Appendix 1 shows conventions for presentation of data in outputs.

The templates provided with this SAP describe the presentations for this study and therefore the format and content of the summary tables, listings, and figures (TLFs) to be provided by Biostatistics.

Note that verbatim terms, specifications (for example the reason a specific assessment was not done) and all variables in the TLF shells that contain the suffix (eCRF) contain verbatim text that may include spelling mistakes. Verbatim text will be presented in the listings "as is" and no manual "hard-coding" corrections of such data will be made.

9. DISPOSITION AND WITHDRAWALS

All subjects who provide informed consent will be accounted for in this study.

The number and percentage of subjects in each disposition category will be presented; there will be no inferential analysis of subject disposition data.

Disposition of all enrolled but not randomized subjects will be tabulated according to screen failure/run-in failure, including primary reason for screen/run-in failure (pretreatment event, major protocol deviation, lost to follow-up, voluntary withdrawal, study termination, did not meet entrance criteria, other) as entered on the electronic case report form (eCRF).

Disposition of all randomized subjects will be tabulated by study phase, treatment group, pooled AZM (for DB and Withdrawal phases only) and overall. Treatments for DB phase are Losartan, AZM low dose, AZM intermediate dose, AZM high dose. Treatments for Withdrawal phase are Placebo, Losartan, AZM low dose, AZM intermediate dose, AZM high dose. Treatments for OL phase are AZM alone, AZM plus additional antihypertensive.

Primary reasons for discontinuation of study drug/visits, as entered on the eCRF, will be tabulated by phase and treatment group; the reasons include adverse event, major protocol deviation, lost to follow-up, voluntary withdrawal, study termination, pregnancy, lack of efficacy, PI discretion and other.

Major protocol deviations will be summarized for RND by phase, treatment group, pooled AZM (for DB and Withdrawal phases only) and overall. Protocol deviations will be presented in a data listing. Also, violation of Inclusion/Exclusion criteria will be listed for RND.

The number of subjects included in each analysis population will be summarized by phase, treatment group, pooled AZM (for DB and Withdrawal phases only) and overall.

Subject disposition, study discontinuation and study visit dates and times will be listed based on RND.

Document: 2014-000674-18 Statistical Analysis Plan Version 7.0 Version Number: 7.0

Version Date:

13JAN2020

Township No. 00 TB B0040 Building 5

Template No.: CS_TP_BS016 Revision 5 Reference: CS_WI_BS005

Effective Date: 01Apr2018

Author:

10. DEMOGRAPHIC AND OTHER BASELINE CHARACTERISTICS

Demographic data and other baseline characteristics will be presented based on RND.

Statistical testing will be carried out and the p-value will be reported for demographic or other baseline characteristics. T-test will be done for continuous variables and Chi-square test will be done for categorical variables.

The following demographic and baseline characteristics will be summarized using descriptive statistics and pvalue for each study phase (DB, Withdrawal, OL) by treatment group, pooled AZM (for DB and Withdrawal phases only) and overall:

- Age (years)
- Tanner Stage (<3, ≥3)
- Race
- Race Group (Black or African American, Non- Black or African American)
- Ethnicity
- Gender
- Height (cm)
- Weight (kg)
- Weight Group (<50 kg, ≥50 kg)
- Body Mass Index (BMI)
- Diagnosis of Chronic Kidney Disease
- Renal Transplant
- Hypertension Diagnosis (Primary or Secondary Hypertension)
- **Baseline Sitting DBP**
- **Baseline Sitting SBP**
- **Baseline Standing DBP**
- **Baseline Standing SBP**
- Baseline ABPM DBP
- Baseline ABPM SBP
- **Female Reproductive Status**
- **Current Hypertensive Medication**
- Glomerular Filtration Rate

All individual demographic and baseline characteristics will be listed by site and subject number.

11. MEDICAL HISTORY

Hypertension and other relevant Medical History information are collected on eCRF Medical History – Hypertension and Medical History pages and will be presented for the SAF.

2014-000674-18 Statistical Analysis Plan Version 7.0 7.0 Document: Version Number: Author: Version Date: 13JAN2020

Template No.: CS_TP_BS016 Revision 5 Reference: CS_WI_BS005

Effective Date: 01Apr2018

- Other relevant Medical History will be coded using Medical Dictionary for Regulatory Activities (MedDRA) Version 20.0 or higher.
 - Medical History conditions are defined as those conditions which stop prior to or at Screening.
 - Other relevant Medical History will be presented by system organ class (SOC) and preferred term (PT).

Hypertension and other relevant medical history will be summarized for subjects in each study phase (DB, Withdrawal, OL) by treatment group, pooled AZM (for DB and Withdrawal phases only) and overall. A list of medical history per subject will be presented.

12. MEDICATIONS

Medication History includes medications that stopped at or within 30 days prior to signing of informed consent (Informed consent date > medication end date ≥ Informed consent date -30).

See Appendix 2 for handling of partial dates for medications.

For Double Blind Phase:

Concomitant medications include medications started at or within 30 days prior to signing of informed consent through end of the double blind phase (informed consent date -30 ≤ medication start date ≤ end of double blind study date) or ended before the first dose of the study medication in the withdrawal phase as well as medications started before 30 days prior to signing of informed consent but stopped on at or after signing of informed consent (medication start date< informed consent date -30 and medication end date≥ informed consent date).

For Withdrawal phase:

Concomitant medications include medications started prior to, on or after the first dose of study medication in the withdrawal phase and ended on or after the date of first dose of study medication in the withdrawal phase or were ongoing till the end of the withdrawal phase.

For Open Label:

Concomitant medications include medications started prior to, on or after the first dose of study medication in the Open Label phase and ended on or after the date of first dose of study medication in the Open Label phase or were ongoing till the end of the Open Label phase.

Medication History and Concomitant Medication information for Single or Double-Blind phase are collected on the concomitant medication page in the eCRF and concomitant medication information for Open Label phase is collected on concomitant medication – open label page in the eCRF. They will be presented for the SAF and coded using World Health Organization Drug Dictionary (WHO-DD).

Medication History and Concomitant Medications will be presented by treatment group for different phases

7.0 Document: 2014-000674-18 Statistical Analysis Plan Version 7.0 Version Number: Author: Version Date: 13JAN2020

Template No.: CS_TP_BS016 Revision 5 Reference: CS_WI_BS005

Effective Date: 01Apr2018

based on Safety population. The summary of Medication History and Concomitant Medication will be provided by Therapeutic Classification (2nd level of ATC) and preferred medication name. Therapeutic Classification will be sorted alphabetically. Preferred Medication Names are sorted by decreasing total number of subjects. Preferred Medication Names are sorted by decreasing total number of subjects.

In the summaries, subjects experiencing more than one medication within the same therapeutic class and preferred name will be counted only once.

Concomitant medications will be listed for the RND.

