6.1.5 Open-Label Phase

Subjects will receive their first dose of OL AZM in the clinic and study drug will be dispensed at Week 8/Visit 9 after the final trough vital sign measures of the Withdrawal Phase are recorded. Each subject will also be provided with a home blood pressure monitoring (HBPM) device and a BP diary so that daily BP measures can be recorded and reviewed by the investigator during the OL Phase (see [Section 9.1.16](#)).

Instructions for drug administration during the OL Phase will be the same as during the double-blind (DB) phases; ie, study medication will be administered orally with water, at an agreed upon (by the site and subject) consistent time of day, with or without food, and will be administered in the clinic on days when a visit is scheduled.

[figure not shown]
Throughout the OL Phase, subjects will be treated to achieve and maintain a target BP of <90th percentile for age, gender, and height. For subjects with CKD, a lower BP target may be utilized at the investigator's discretion. Evidence suggesting lower BP targets are appropriate and improve renal outcomes in this patient population is summarized in [Section 6.2.6](#).

All subjects will start the OL Phase receiving AZM 10 mg which can be titrated to higher dose(s) (up to 40 mg for subjects <50 kg or up to 80 mg for subjects \geq 50 kg), and additional antihypertensive medications can be added if needed to achieve target BP. If add-on therapy is needed, the type of medication added (eg a calcium channel blocker, such as amlodipine, a diuretic, such as hydrochlorothiazide, or a beta-blocker such as metoprolol) will be determined per the investigator's clinical judgment. The recommended treatment algorithm for the OL Phase is provided in [Figure 6.b](#).

In the event that down-titration or temporary or permanent discontinuation of antihypertensive medication is indicated, dose reduction or discontinuation should begin with the additional antihypertensive drug(s) first, before the dose of AZM is reduced or discontinued. During the OL Phase subjects may continue participation in the study if AZM is temporarily discontinued for less than 2 weeks. Treatment with a dose of AZM that is above the highest dose allowed for the body weight category (ie, to 80 mg in a subject <50 kg) is not allowed.

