7.3.1 Washout/Placebo Run-in, Double-Blind and Withdrawal Phases: Excluded Medications

The following medications will be prohibited during the Washout/Run-in, DB and Withdrawal Phases. When appropriate, medications may be tapered-off gradually before double-blind treatment is initiated, but a minimum drug-free period of at least 7 days is required before randomization.

- All classes of antihypertensive drugs, including drugs that have an effect on BP but are prescribed for another indication, with the exception of concomitant medications listed in [Section 7.3.2](#).
- Lithium.
- Monoamine oxidase inhibitors.
- Tricyclic antidepressants.
- Amphetamines or their derivatives (see [Section 7.3.2](#) for exceptions).
- Dopamine agonists.

- Atypical antipsychotic agents.
- Anticonvulsants.
- Trazodone.
- Nitrates.

7.3.2 Washout/Placebo Run-in, Double-Blind and Withdrawal Phases: Concomitant Medications Allowed Conditionally

Conditional use of the following medications will be allowed in the Washout/Run-in, DB and Withdrawal Phases. These medications must be at a stable dose through the Week 8 visit (end of withdrawal phase) without changes unless absolutely medically necessary. Routine weaning and/or dose adjustments can be made during the open-label phase of the study:

- Diuretics, including loop-diuretics (eg, furosemide): Stable dose allowed if indicated for the treatment of oedema/CKD.
- Steroids: Systemic use is allowed at stable low/maintenance dose up to hydrocortisone 12 mg/m²/day (or the appropriate dose equivalent if other steroid is administered) for replacement therapy in subjects with adrenal insufficiency or other medical conditions. Immunosuppressive treatment in post renal transplant subjects or in subjects with glomerular disease with prednisolone is allowed at a maximum dose of 15 mg/m² (0.5 mg/kg) (or the appropriate dose equivalent if other steroid is administered). Doses need to be stable at least 30 days prior to Screening as mandated by inclusion criterion #8Topical and inhaled corticosteroids (eg, for treatment of asthma) are also allowed at stable maintenance doses.
- Central nervous system (CNS) stimulants: Stable dose allowed if indicated for treatment of attention deficit hyperactivity disorder.

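### The Withdrawal Phase concomitant-medication definition in SAP section 12 has no upper limit on start date, so read literally it takes in drugs first started in open label (a minor correction to one descriptive table)

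*SAP*

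**What the plan says.** SAP section 12 defines concomitant medication separately for each phase.

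- **Withdrawal Phase.** The definition covers "medications started prior to, on or after the first dose of study medication in the withdrawal phase and ended on or after the date" on which withdrawal dosing began. An alternative limb admits drugs that "or were ongoing till the end of the withdrawal phase".
- **Double-Blind Phase.** The main clause covers medications "started at or within 30 days prior to signing of informed consent through end of the double blind phase", restated as "informed consent date -30 ≤ medication start date ≤ end of double blind study date". Two further clauses deal with drugs that stopped before the first withdrawal dose and with long-standing drugs still in use at consent.
- **Open-Label Phase.** The Withdrawal pattern is repeated. The missing cap does less harm here because no later treatment phase follows.

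The same section says that blinded-phase and open-label medications are collected on different eCRF pages. It plans summaries by phase and treatment group in the safety population, by therapeutic class and preferred name.

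Protocol section 7.3.1 prohibits, through the Withdrawal Phase, "All classes of antihypertensive drugs, including drugs that have an effect on BP but are prescribed for another indication", apart from the conditional exceptions in section 7.3.2. In open label, Protocol section 6.1.5 says "additional antihypertensive medications can be added if needed to achieve target BP", and gives a calcium channel blocker, a diuretic and a beta-blocker as examples.

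**The concern.** The Withdrawal Phase runs from Week 6 to Week 8, the interval over which the primary endpoint is measured. Antihypertensives are largely barred in it and freely permitted straight after it. A reader would use the Withdrawal Phase medication table to check whether other blood-pressure drugs were in use during those two weeks. If the table is built from the rule as written, add-ons started in open label could be counted under the AZM and placebo withdrawal arms. The table would then suggest prohibited use that never happened.

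The wording also differs from the SAP's own practice. The main Double-Blind clause caps the start date at the end of its phase. For adverse events, SAP section 16.1 closes the Withdrawal Phase at the first open-label dose and has a separate provision for subjects who do not enter open label. Medications and adverse events for the same phase therefore have different boundaries, and no reason is given.

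**Working it through.** The plan states no figure on this point, so the check applies the written rule to example records.

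**Inputs.** Visit weeks come from the Protocol schedule (Table 9.b) and SAP Appendix 1, converted as day = 7 × week + 1:
- first withdrawal dose, Week 6: 7 × 6 + 1 = Day 43
- first open-label dose, Week 8: 7 × 8 + 1 = Day 57
- end of open label, Week 52: 7 × 52 + 1 = Day 365
- consent at the nominal screening day, Day -28

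**Rules.**
- Withdrawal, as written: any start date, and (stop ≥ Day 43 or ongoing).
- Withdrawal, with cap: start < Day 57, and (stop ≥ Day 43 or ongoing).
- Double-Blind: any of its three clauses.

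**Result by record.**

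| Record | Double-Blind | Withdrawal as written | Withdrawal with cap |
|---|---|---|---|
| Long-standing (start Day -400), ongoing | yes | yes | yes |
| Days 20 to 30 | yes | no | no |
| Days 45 to 50 | no | yes | yes |
| Started Day 57, ongoing | no | **yes** | no |
| Started Day 85 (Week 12), ongoing | no | **yes** | no |
| Days 85 to 300 | no | **yes** | no |
| Days 200 to 207 | no | **yes** | no |

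**Over all open-label start days.** There are 365 - 57 + 1 = 309. Under the written rule 309 of 309 qualify for the Withdrawal Phase; with the cap, 0 of 309. In the table, the records that began before or during the Withdrawal Phase are classified the same way by both versions.

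**One assumption.** For an open-label drug with a recorded stop date the result follows from the text alone. For one with no stop date, the check counts an ongoing record as meeting the rule. A strict reader could say that such a drug was not ongoing to the end of the Withdrawal Phase because it had not yet begun. The short course on Days 200 to 207 does not depend on this.

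**Does Appendix 2 supply the limit?** No. Its row for known start and known stop dates has no upper limit on start. Other rows refer to the end of treatment, which is not defined by phase.

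**The case against.** The strongest reply is that the SAP has other features that would keep open-label drugs out of the table.

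- **Visit conventions.** Appendix 1 sets the Withdrawal Phase as Visit 8 to Visit 9 and names concomitant medications among the Visit 9 data used as the last Withdrawal Phase visit. An add-on first recorded at Week 12 falls after that. This shows the intent, but it does not say that later-started drugs are excluded, and section 12 does not refer to it.
- **Separate eCRF page.** A programmer who built the Withdrawal table from the blinded-phase page alone would avoid the error. Section 12 does not make page part of the definition. Page and phase are also not the same thing, since the open-label rule takes in drugs started earlier, which would sit on the blinded-phase page. That shows blinded-page records feeding the open-label table; it does not show the reverse flow, so selection by page remains possible but unstated.
- **Interim lock.** Under SAP section 4.2 the Double-Blind and Withdrawal outputs come from data locked for those two phases. Children enrolled early may already have open-label records by then, and the SAP does not say whether those records are set aside.

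These points stand as reasons why literal misclassification is less likely. They do not repair the definition.

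A reader might also infer that real prohibited use could no longer be separated from open-label use. The documents do not support that. Section 12 plans a medication listing for all randomized subjects, section 6.1 provides for start and stop study days, and section 9 summarizes major deviations by phase and treatment group and lists deviations.

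**Conclusion.** The point holds as a minor drafting error. Read literally, the Withdrawal Phase definition admits every drug started in open label that has a stop date, and it is out of line with two neighbouring rules in the same SAP. Only the descriptive Withdrawal Phase medication summary is affected.

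Two stronger readings are not supported:

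- **That the primary result is compromised.** The ANCOVA in SAP section 15.1.3 uses treatment, Tanner stage, race, weight group and Week 6 seDBP; concomitant medication does not enter it. Section 5.5 says that per-protocol exclusions may include taking prohibited medication, but it ties them to deviations identified before database lock, not to this table.
- **That the distortion can be put as a percentage of children or of drug starts.** The documents give no rate of open-label add-on use. Comparing phase lengths would assume a constant start rate, which does not suit drugs that are barred in Weeks 6 to 8 and whose first scheduled titration visit is Week 12. Nor is true use in Weeks 6 to 8 necessarily nil, because Protocol section 7.3.2 allows stable diuretics for oedema or chronic kidney disease. A diuretic in the table may be neither an artefact nor a violation.

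The 309 of 309 result describes what the rule permits. It does not predict how many records would be misplaced, which depends on how the table is programmed.

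**What to change.** Add to the Withdrawal Phase definition in SAP section 12: *and started before the first dose of open-label study medication (or on or before the last withdrawal dose for subjects who do not enter open label)*. Keep the existing stop-date and ongoing conditions.

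This puts the end of the phase at the first open-label dose, where section 16.1 already puts it for adverse events in subjects who continue. The cost is one clause and the matching line of code. No planned test or estimate changes. Stating in Appendix 2 what the end of treatment means for each phase would be a useful companion edit, but the correction does not depend on it.
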